4.3. Overall Time and Events Schedule

The Schedule of Events is displayed in Tables 1 and 2. Greater detail concerning the schedule of events can be found in the protocol.

Table 1 Schedule of Events - Screening to End of Study

Study Period	Screening						Trea	tment P	eriod					
Week	up to Week -4	BL/1	4	8	12	16	20	24	28	32	36	40	44	48
Informed Consent	X													
Inclusion/Exclusion	X	X												
Medical History	X													
Full Physical Exam	X	X	X		X			X						X
Brief Physical Exam				X		X	X				X			
Vital Signs ^a	X	X	X	X	X	X	X	X	X	X	X	X	X	X
Weight	X	X	X	X	X	X	X	X	X	X	X	X	X	X
Safety Lab Assessments	X	X ^b	X	X	X			X			X			X
CCI														
Whole Blood (Genotyping CCI) ^c	X													
Height and Ulnar Length	X	X			X			X			X			X
CCI														
CCI														
ECG	X ^f				X			X			X			X
Holter ECG	X ^f													X
ЕСНО	X ^f				X			X			X			X

Version 1.0 (20 April 2017) Page 10 of 40

Study Period	Screening		Treatment Period										
Week	up to Week -4	BL/1	BL/1 4 8 12 16 20 24 28 32 36 40 44 48										
Study Drug Infusion			Once Weekly										
Conmed/Therapy						Сс	ontinuou	s					
AE Assessment						Сс	ntinuou	s					

Footnotes for Table 1 Schedule of Events: Screening through Week 48

Functional assessments, \overline{CCI} , ECG, Holter ECG, and ECHO have a ± 2 weeks window

- ^a For infusion visits, vital signs are to be collected within approximately 30 minutes prior to infusion and approximately 5, 30, and 60 minutes after the end of the infusion. If the patient has not experienced an infusion reaction after the first year of treatment, vital signs may be collected only 30 minutes after the end of the infusion.
- ^b Blood samples for the safety laboratory assessments must be obtained within 2 weeks prior to the Baseline/Week 1 visit, and results must be available prior to dosing at Baseline/Week 1. If more than 2 weeks have elapsed since the collection of blood samples for the Screening safety laboratory assessments, it must be repeated. If less than 2 weeks have elapsed since the collection of blood samples for the Screening safety laboratory assessments, additional safety laboratory assessments do not need to be performed.
- ^c Patients may start dosing based on local genotyping results provided that these results fulfill the required inclusion criteria; however, all patients must undergo genetic testing to confirm the exon 51 skippable mutation CCI.

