- ^c Patients may start dosing based on local genotyping results provided that these results fulfill the required inclusion criteria; however, all patients must undergo genetic testing to confirm the exon 51 skippable mutation CCI.
- Screening ECG, Holter ECG, and ECHO may be performed at any time during the Screening period; however results must be available on Day 1, prior to dosing.
- g In the event of early termination prior to Week 96, the Week 96 assessments should be completed as the Early Termination visit.
- ^h End of Study visit should occur within 4 weeks after last dose

Version 1.0 (20 April 2017) Page 13 of 40

Table 2 Schedule of Events - Safety Extension Period

Study Period	Safety Extension Period (Starting at Week 97 and continuing until the product is commercially available or until patients can transition into a separate eteplirsen study)						
Week	120	144					
Full Physical Exam	X	X					
Vital Signs ^a	Wee	Weekly					
Weight	Every 4	Every 4 Weeks					
Safety Lab Assessments	X	X					
CCI							
CCI							
ECG	X	X					
ЕСНО	X	X					
Study Drug Infusion	Once V	Once Weekly					
Conmed/Therapy	Conti	Continuous					
AE Assessment	Conti	Continuous					

Functional assessments, CCI, ECG, Holter ECG, and ECHO have a ±2 weeks window

Version 1.0 (20 April 2017) Page 14 of 40

^a For infusion visits during the Safety Extension Period, vital signs are to be collected within approximately 30 minutes prior to infusion and approximately 5, 30, and 60 minutes after the end of the infusion. If the patient has not experienced an infusion reaction in the past year of treatment, vital signs may be collected only 30 minutes after the end of the infusion.

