5.5.7.2. Laboratory Measurements

Descriptive statistics for continuous hematology, clinical chemistry, urinalysis, and coagulation laboratory measurements will be presented by time point. Summary statistics for each lab parameter and time point as well as the change from Baseline to the time point will be displayed. For each numeric laboratory parameter, box plots of values over time will be generated. A shift table will compare N (%) of low, normal, and high status of the lab values at Baseline to their worst value post-Baseline through Week 96. A table summarizing the frequency and percent of subjects meeting the predefined markedly abnormal criteria at each visit will be presented. The predefined markedly abnormal criteria are defined below in Tables 3-1, 3-2, and 3-3. All laboratory values will be displayed in a data listing.

Table 3-1 Predefined Markedly Abnormal Hematology Laboratory Values

Test	Unit	Markedly Abnormal Criteria
Hematocrit	1	< LLN
Hemoglobin	g/L (or mmol/L)	< LLN
Red blood cell count	T/L	< LLN
White blood cell count	count/L	$>1.5 \times ULN \text{ or } < LLN$
Platelet count	10^3/L	< 150 or < 200 with a decrease of at least 100
Basophils (abs)	count/L	> ULN or < LLN
Eosinophils (abs)	count/L	> 1.5xULN or < LLN
Lymphocytes (abs)	count/L	< LLN
Monocytes (abs)	count/L	< LLN
Neutrophils (abs)	count/L	>1.5 × ULN or < 1000

ULN = upper limit of normal

LLN = lower limit of normal

abs = absolute

Table 3-2 Predefined Markedly Abnormal Chemistry Laboratory Values

		Predefined	Change	
Test	Unit	Decrease	Increase	Markedly Abnormal Criteria
Fasting blood glucose*	mmol/L	3.1	3.2	
Urea (BUN)	mmol/L			Value >1.5 × Baseline Value AND > ULN
Creatinine	μmol/L		35	Value >1.5 × ULN
Sodium	mmol/L	8	8	
Potassium	mmol/L	1.1	1.0	Value >5.5 mmol/L or < 3 mmol/L
Chloride	mmol/L	9	8	
Uric acid	μmol/L			>1 × ULN
Calcium#	mmol/L	0.30	0.30	
Total cholesterol	mmol/L		1.73	
AST (SGOT)	U/L			Value ≥3 × Baseline Value
ALT (SGPT)	U/L			Value ≥2 × Baseline Value
Gamma GT (GGT)	U/L			Value >3 × Baseline Value OR > ULN
Alkaline phosphatase	U/L			Value >1.5 × ULN
Total protein@	g/L	11	10	
Albumin	g/dL	1 g/dL decrease or	1 g/dL increase	Value < LLN or > ULN
Total bilirubin ^{&}	μmol/L		10	Value >1.5 × ULN
LDH	U/L			Value ≥2 × Baseline Value
Creatine phosphokinase	U/L			Value ≥2 × Baseline Value
Triglycerides	mmol/L	_	2.88	
Cystatin C	mg/L			>ULN

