^{*}Convert to SI unit by multiplying mg/dL value by 0.0555; *multiply mg/dL value by 0.25; @multiply g/dL value by 10; &multiply mg/dL value by 17.1.

LLN = lower limit of normal

ULN = upper limit of normal

TEMA = treatment-emergent markedly abnormal

Table 3-3 Predefined Marked	v Abnormal Urinalysi	s Laboratory Values
-----------------------------	----------------------	---------------------

	Predefined Change		
Test	Decrease	Increase	Markedly Abnormal Criteria
Protein in urine			>1+
KIM-1*			> ULN

^{*} Adult normal ranges provided by the laboratory will be used for all subjects as no pediatric ranges are available.

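### SAP Table 3-1: the printed units for the low neutrophil and platelet cut-offs do not fit their numerals, so read literally neither rule can flag a plausible non-zero count

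*SAP*

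**What the plan says.** SAP section 5.5.7.2 sets the markedly abnormal haematology criteria in Table 3-1. Two of its ten rows use absolute numbers:

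- "Neutrophils (abs) count/L >1.5 × ULN or < 1000"
- "Platelet count 10^3/L < 150 or < 200 with a decrease of at least 100"

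The other eight rows use only the laboratory's LLN or ULN, for example "Red blood cell count T/L < LLN". Those criteria work whatever unit is printed beside them.

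The criteria feed one visible output: "A table summarizing the frequency and percent of subjects meeting the predefined markedly abnormal criteria at each visit will be presented". The same section plans a low/normal/high shift table, which uses reference ranges instead of Table 3-1 and compares Baseline with "their worst value post-Baseline through Week 96".

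The only unit conversions given are in the footnote to Table 3-2, beginning "Convert to SI unit by multiplying mg/dL value by 0.0555". They cover chemistry tests. Nothing else in the SAP or protocol gives a unit or a conversion for cell counts.

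**The concern.** A cut-off of 1000 is natural for neutrophils per microlitre, and cut-offs of 150 and 200 are natural for platelets in thousands per microlitre. The table prints both rows per litre. Either the unit or the numeral is wrong, and a programmer who works from the SAP has to guess which.

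The incidence of clinical laboratory abnormalities is a stated safety endpoint (Protocol 7.3.1 and 13.8.1), and safety is the primary objective. Protocol 13.8.2.3 commits to frequency tables of predefined abnormal values, which this SAP table delivers. SAP 5.5.7.1.1 also lists leukopenia and neutropenia, and thrombocytopenia under coagulopathy, as adverse events of special interest. The laboratory rules that match those events should therefore work.

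Neither row has an LLN rule as a back-up. Low-count events can be missed or grossly over-counted, depending on how the rows are programmed.

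**Working it through.** **Inputs.** The cut-offs and units are from SAP Table 3-1. Visits are from "Table 1 Schedule of Events - Screening to End of Study" and "Table 2 Schedule of Events - Safety Extension Period". The sample size of about 20 is from SAP 5.1. The documents give no haematology values, so I assume neutrophils of 0.1 to 20 ×10^9/L and platelets of 10 to 600 ×10^9/L. Lower floors of 0.01 and 1 ×10^9/L are a sensitivity check. The plan states no figure of its own to reproduce.

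**Step 1: convert the printed cut-offs.**

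| Cut-off | Per litre, as printed | Per µL | ×10^9/L | Same numeral in count/µL or 10^3/µL | Ratio |
|---|---|---|---|---|---|
| Neutrophils 1000 | 1,000 | 0.001 | 0.000001 | 1.0 ×10^9/L | 10^6 |
| Platelets 150 | 150,000 | 0.15 | 0.00015 | 150 ×10^9/L | 10^6 |
| Platelets 200 | 200,000 | 0.2 | 0.0002 | 200 ×10^9/L | 10^6 |
| Platelet fall of 100 | 100,000 | 0.1 | 0.0001 | 100 ×10^9/L | 10^6 |

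**Step 2: apply each possible reading.**

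(a) *Units taken literally.* Lowest assumed count divided by the cut-off:

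- Neutrophils: 0.1×10^9 / 10^3 = 100,000.
- Platelets, 150 branch: 10×10^9 / (150×10^3) = 66,667.
- Platelets, 200 branch: 10×10^9 / (200×10^3) = 50,000. The fall of 100 is met by almost any decrease, but the condition of being below 200 is never met.

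With the lower floors the ratios are still 0.01×10^9 / 10^3 = 10,000; 1×10^9 / (150×10^3) = 6,667; and 1×10^9 / (200×10^3) = 5,000. No non-zero count is flagged, so the result does not depend on the range chosen.

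(b) *Units ignored, data in 10^9/L.* The platelet rule works. Neutrophil values of 0.1 to 20 are all below 1000, so 100% of patients tested are flagged at every visit.

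(c) *Units ignored, both rows in cells/µL.* The neutrophil rule works. The lowest assumed platelet count is 10×10^9/L = 10,000/µL, and 10,000 / 150 = 67, so no platelet count is flagged.

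(d) *Neutrophils in cells/µL and platelets in 10^3/µL.* Both rules discriminate. Neutrophils of 0.99 ×10^9/L are flagged and 1.0 is not. Platelets of 149 ×10^9/L are flagged; 180 is flagged from a baseline of 300 but not from 250.

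Of these readings only (d) makes both rows work. It needs a different unit for each row, and neither is the unit printed.

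**Step 3: size of the affected output.** Safety laboratory visits after Baseline are Weeks 4, 8, 12, 24, 36, 48, 72 and 96 (8), plus Weeks 120 and 144 (2), so 10. The maximum is 10 × 20 = 200 patient-visits, plus up to 20 at End of Study. Two of the 10 visits lie beyond the shift table, which stops at Week 96.

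**The case against.** The strongest objection is that the plan may be correct and the text reading faulty. Reading (d) is the printed table with one micro sign restored in each cell. Seven cells in the unit column (six in count/L and one in 10^3/L) would be explained by a single loss of that character, and other symbols near these tables came through unevenly. This cannot be excluded. It is less likely because the micro sign survives in all three µmol/L cells of Table 3-2, in the same section. That hemoglobin and red cells carry true per-litre units adds little, since those cells would hold no micro sign either way.

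A second objection is that no harm is shown. Zero flags would require someone to rescale the data to match the label, and flagging every patient for low neutrophils would be noticed on first output. That is fair: misclassification is possible but not demonstrated. A rule that flags nobody, however, looks the same as a clean safety result.

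Third, low values are visible elsewhere: in by-visit statistics with the minimum, box plots, listings, laboratory range flags (Protocol 10.3.3), the shift table to Week 96, the white cell and lymphocyte rules in the same table, and the adverse event summaries. This also stands and limits the weight of the point. But none of these counts patients against the two cut-offs. An abnormal test is listed as an adverse event when it changes care (Protocol 11.2.1), so adverse event tables need not capture every low count.

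Finally, 200 patient-visits is a ceiling. Patients who move to commercial drug or another study will not reach Weeks 120 and 144.

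**Conclusion.** The point holds on the text as it reads. Both rows carry cut-offs 10^6 below the same numerals per microlitre, nothing elsewhere corrects them, and read literally neither low-side rule can flag a plausible non-zero count.

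The damage is narrow: the low-side neutrophil rule and the platelet rule in the by-visit markedly abnormal table. The neutrophil rule above 1.5 × ULN and all other LLN or ULN rules are unaffected. SAP 5.4.6 defines a treatment-emergent laboratory abnormality by reference to the same section, but no separate output based on it is visible. At Weeks 120 and 144 the by-visit table is the only visible laboratory summary that counts patients with low values, so the error matters most there.

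The study is descriptive with about 20 patients. This is a correctable error in one table and should be fixed, but it does not threaten the conclusions. Confidence is medium, for two reasons: the source PDF may show a micro sign that the text lacks, and the analysis dataset's unit is not stated.

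**What to change.** 1. Check the printed SAP for a micro sign in the Table 3-1 unit column. If it is there, the table needs no correction.
2. If the units are as they read here, reconcile unit and numeral in the two rows against the central laboratory's reporting units, keeping the sponsor's numerals. The evident reading, for the sponsor to confirm, is neutrophils below 1000/µL (1.0 ×10^9/L), and platelets below 150 ×10^3/µL, or below 200 ×10^3/µL with a fall of at least 100 ×10^3/µL (150, 200 and 100 ×10^9/L).
3. State the analysis-dataset unit beside each absolute cut-off.
4. Check the programmed derivation with test values on either side of each cut-off.

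The cost is two table cells and a programming check. No new data are needed.

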5. STATISTICAL METHODS

5.1. Sample Size

There is no formal sample size calculation. The sample size is based on qualitative considerations and is sufficient to provide safety evaluation of eteplirsen in the studied population. Approximately 20 patients will be enrolled in this study.

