5.4.6 Definitions and Terminology

Study Day

Study day will be defined as Event Date – Study Day 1 + 1

Study Day 1

Day 1 is defined as the date of first dose of eteplirsen at the Week 1 visit during the 4658-204 Study.

Days on Study

Days on Study is the number of days from Study Day 1 to the date of study completion or early termination as recorded on the END OF STUDY VISIT CRF.

Days on Study Drug

Days on Study Drug is the number of days from the date of first dose to the date of the last dose of the specific study medication as recorded on the STUDY DRUG ADMINISTRATION CRF.

Planned Number of Infusions

The planned number of infusions will be based on the subject's last local site visit. The subject will be expected to receive an infusion once weekly up until their last local site

visit. If a subjects completes 100 local site visits and then completes or discontinues the study the planned number of infusions will be 100.

Treatment Group

All subjects received 30 mg/kg weekly of eteplirsen and will be analyzed in the same group.

Time Since DMD Diagnosis

The time since DMD diagnosis, in months, will be calculated as Month and Year of first dose – Month and Year of diagnosis

Treatment-Emergent Adverse Event

An AE is considered treatment-emergent if it occurs on or after the initiation of the first dose of eteplirsen and within 28 days of last dose.

Treatment Related Adverse Event

A treatment-related AE is any adverse event reported on the CRF that is marked as definitely, probably or possibly related to study drug. Additionally, it is assumed that an AE without a relationship is treatment-related.

Treatment-Emergent Laboratory Abnormality

[figure not shown]
A treatment-emergent laboratory abnormality is defined as any laboratory abnormality (as defined in section 5.5.7.2) that occurs following the initiation of eteplirsen which was not present at Baseline.

Prior Medication

A prior medication is any medication taken prior to the first study drug administration.

Concomitant Medication

A concomitant medication is any medication that is taken on or after the first study drug administration.

Final Analyses

An analysis will be performed once all subjects complete their End of Study visit and the resulting clinical database has been cleaned, quality checked and locked through the data cut.

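### The GGT criterion in SAP Table 3-2 joins its two conditions with OR, so one count mixes borderline or pre-existing elevations with large rises, and the 3 × Baseline condition has no effect above ULN

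*SAP*

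**What the plan says.** SAP section 5.5.7.2, Table 3-2, sets the GGT criterion as "Value >3 × Baseline Value OR > ULN". The section states how the criteria are used: "A table summarizing the frequency and percent of subjects meeting the predefined markedly abnormal criteria at each visit will be presented".

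Other rows of the chemistry table serve as comparators:

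- Urea is the only other row that combines a multiple of Baseline with ULN, and it joins them with AND: "Value >1.5 × Baseline Value AND > ULN".
- Alkaline phosphatase, total bilirubin and creatinine carry "Value >1.5 × ULN" in the criteria column.
- AST, ALT, LDH and creatine phosphokinase use a multiple of Baseline alone.
- Uric acid and cystatin C use a bare ULN limit, as KIM-1 does in Table 3-3.

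Two other provisions bear on the point. Section 5.5.7.2 also plans a shift table: "A shift table will compare N (%) of low, normal, and high status of the lab values at Baseline" is set against the worst later value through Week 96. Section 5.4.6 defines a treatment-emergent laboratory abnormality, by reference to section 5.5.7.2, as one "that occurs following the initiation of eteplirsen which was not present at Baseline". The sentence that sets up the by-visit table does not say that this condition is applied. The abbreviation TEMA is expanded beneath Table 3-2, but the text of section 5.5.7.2 does not use it. Nothing in the SAP explains the OR in the GGT row.

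**The concern.** A criterion with a multiple-of-Baseline part and a ULN part looks designed to pick out a marked rise. Joined by OR, it does not. A patient whose GGT has been stable slightly above ULN since before dosing meets it at every visit. So does a patient who drifts from just under to just over ULN, and so does one with a large rise, and the table shows all three as the same count. The only extra patients the 3 × Baseline part can bring in are those whose value is not elevated.

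Incidence of laboratory abnormalities is a safety endpoint (protocol section 7.3.1), and drug-induced hepatotoxicity is a named adverse event of special interest (SAP section 5.5.7.1.1). With a single arm, there is no control rate against which to discount background GGT flags. At stake is whether one row of a descriptive table can be interpreted. No hypothesis test depends on it.

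**Working it through.** The documents give no figure on this point to reproduce: the SAP states "There is no formal sample size calculation", and nothing predicts how many patients will be flagged. The check is therefore of the logic, followed by an illustration of size.

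**Step 1. Thresholds.** Let *b* be Baseline and *v* the on-study value, both in units of ULN.

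- OR flags *v* > min(3*b*, 1).
- AND flags *v* > max(3*b*, 1).

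| Baseline (× ULN) | OR threshold | AND threshold | Unchanged value flagged? (OR / AND) | Value of 1.01 × ULN flagged? (OR / AND) |
|---|---|---|---|---|
| 0.1 | 0.3 | 1.0 | no / no | yes / yes |
| 0.2 | 0.6 | 1.0 | no / no | yes / yes |
| 0.3 | 0.9 | 1.0 | no / no | yes / yes |
| 0.5 | 1.0 | 1.5 | no / no | yes / no |
| 0.8 | 1.0 | 2.4 | no / no | yes / no |
| 1.0 | 1.0 | 3.0 | no / no | yes / no |
| 1.2 | 1.0 | 3.6 | yes / no | yes / no |
| 1.5 | 1.0 | 4.5 | yes / no | yes / no |

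**Step 2. What the 3 × Baseline part adds under OR.** The added set is *v* > 3*b* with *v* ≤ 1, which requires *b* < 1/3. Enumerating *b* and *v* from 0.01 to 5.00 × ULN confirms this: every value flagged only by that part is at or below 1.00 × ULN, and the largest Baseline involved is 0.33 × ULN. For a Baseline of ULN/3 or more, that part adds nothing.

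**Step 3. Examples, with an assumed ULN of 40 U/L.** Through Week 96 the schedule has eight post-Baseline safety laboratory visits (Weeks 4, 8, 12, 24, 36, 48, 72 and 96).

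- Baseline 45 and unchanged: flagged at all eight visits under OR, never under AND.
- Baseline 38 to 41: flagged under OR; not under AND (3 × 38 = 114).
- Baseline 12 to 37, in range: flagged under OR (3 × 12 = 36); not under AND.
- Baseline 45 to 130: flagged under OR. Not flagged under AND, because 3 × 45 = 135, although the rise is 130/45 = 2.9-fold and the value is 130/40 = 3.25 × ULN.

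**Step 4. Per-visit size.** The SAP says "Approximately 20 patients will be enrolled in this study". Let *q* be the assumed proportion of unaffected values above ULN. The expected number flagged is 20*q*, and the chance of at least one is 1 − (1 − *q*)^20.

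| *q* (assumed) | Expected of 20 | Chance of at least one |
|---|---|---|
| 1% | 0.2 | 18% |
| 2.5% | 0.5 | 40% |
| 5% | 1.0 | 64% |

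**Step 5. Repeated visits.** The simulation assumed log-normal values with no drug effect, between-patient SD 0.30–0.40 and within-patient SD 0.15–0.25 on the log scale, ULN at the 97.5th percentile, and eight visits. None of these variances or percentiles is in the documents.

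- Flagged per visit under OR: about 2.5%, or 20 × 0.025 = 0.5 patient.
- Flagged at least once in eight visits: 6–12% under OR (20 × 0.06 = 1.2 to 20 × 0.12 = 2.4 patients), and at most about 0.2% under AND.
- Patients above ULN at Baseline: 68–90% flagged at least once under OR. By construction this group is about 2.5% of patients, or 0.5 of 20.
- Patients flagged only through the 3 × Baseline part: 0.0–0.5% over eight visits.

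**The case against.** **The ULN part may be deliberate.** Bare limits are common in these tables. Uric acid, cystatin C and KIM-1 are markedly abnormal above ULN, hemoglobin is so below LLN, and albumin is so outside either limit. This stands: a low threshold is not in itself a fault peculiar to GGT. It does not explain why a 3 × Baseline condition was added that cannot act above ULN.

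**In-range flags also arise elsewhere.** The AST, ALT, LDH and creatine phosphokinase rows have no ULN condition. This also stands, and under the assumed model such flags are rare for GGT.

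**Treatment emergence is defined.** Section 5.4.6 would remove the patient already above ULN at Baseline, if it were applied. That is partial mitigation: the by-visit table does not state the filter, and the filter would not remove a move from 38 to 41 at an assumed ULN of 40.

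**Other displays show the rise.** Change from Baseline, box plots, the shift table and the full listing remain, and the hepatotoxicity special-interest summaries come from coded adverse events, not from Table 3-2. This stands and limits the weight of the point.

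**AND alone could lose real rises.** This stands. It raises the threshold to 3 × ULN for a Baseline at ULN and misses 45 to 130 in the example. Adding only a row for new elevations would miss that patient too, and the shift table would show high to high.

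A reader might infer that OR is a proven slip for AND. The documents do not show that: the urea row uses a different multiple (1.5), and no text states the intent for GGT.

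**Conclusion.** The logical point holds as written and needs no assumption: under OR the 3 × Baseline condition is redundant above ULN, and the row cannot separate a borderline or long-standing elevation from a large rise. If a simple ULN rule was meant, the second condition is misleading; if a marked rise was meant, OR defeats it. The documents do not settle which.

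The size is modest. The planned table is per visit, where the assumed model gives about 0.5 of 20 patients flagged without any drug effect, and nearly all of that follows from placing ULN at the 97.5th percentile. The 6–12% over eight visits is a cumulative figure that the SAP does not plan to tabulate.

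A reader might go further and infer that the trial's liver findings as a whole would be overstated, or that a real rise could not be seen. The documents do not support that: the effect is confined to one row of a descriptive table, and the other displays and the adverse event summaries do not depend on it.

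**What to change.** The sponsor should confirm which connector was intended for GGT, reconcile the GGT and urea rows or state why they differ, and report GGT in two rows of the by-visit table:

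- (a) more than 3 × Baseline AND above ULN, labelled as the marked rise;
- (b) all values above ULN, with those not above ULN at Baseline counted separately as treatment-emergent under section 5.4.6.

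Row (b) must keep all values above ULN, not only the new ones. Then no above-ULN value is lost, including a rise of less than 3-fold from an already high Baseline.

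The cost is one extra table row with its sub-count. In-range values above 3 × Baseline would no longer count as markedly abnormal, but they remain in the listing and the change-from-Baseline summaries. No new data are needed.
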